4.4 Randomisation and Blinding

Not Applicable.

4.5 Sample Size Determination

This is a confirmatory clinical investigation. The objective is to collect new additional clinical data demonstrating the safety and the performance of the device in the contact-lens wearing population with dry eye symptoms. Consequently, no formal sample size calculation is performed, and it is considered that around evaluable CCI patients is sufficient to reach the clinical investigation objectives.

A total of CCI patients should be enrolled in the study to take into account approximately 10% of drop-out/non-evaluable patients. Evaluable patients will be defined as included patients having received at least one dose of IMD and at least one evaluation of performance.

5 Considerations for Statistical Analysis

The *SAS Viya 3.5 (SAS Studio 5.2 or higher)* will be used for all analysis, unless otherwise specified.

5.1 Analysis Periods

Visit Windowing

All data will be analysed according to the planned visit as collected in the electronic CRF (eCRF).

Data from premature discontinuation visit will be allocated to the next planned visit unless the scheduled visit is performed after discontinuation visit.

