Performance Parameters	
 • CLDEQ-8 self-questionnaire. • Soothing sensation just after IMD instillation (less than 5 minutes) using a 4-point scale. • OSDI self-questionnaire. • Ocular discomfort within the last 48 hours on a Visual Analog Scale (VAS, 0-100) (from 0 [no discomfort] to 100 [maximal discomfort]). • Ocular symptoms throughout the day within the last 48 hours: burning/irritation, stinging/eye pain, itching/pruritus, eye dryness feeling, tearing, foreign body sensation, graded using a 4-point scale. • Contact lens wearing time (hours/day and days/week). • Conjunctival hyperaemia using Mc Monnies photographic scale (0-5) in each eye. • Tears Break Up Time (TBUT) in each eye (in sec). • Total Ocular surface staining according to Oxford 0-15 grading scheme (corneal and conjunctival staining by fluorescein with a yellow filter) in each eye. • Schirmer test (without anesthesia) in each eye (in mm/5 min). • Performance assessment by the investigator using a 4-point scale (very satisfactory, satisfactory, not very satisfactory, unsatisfactory).
Safety Parameters	
 • Ocular AE reporting. • Systemic AE reporting. • Reporting of Device Deficiencies (DD) that may lead to Serious Adverse Event (SAE). • Far BCVA in each eye. • Ocular tolerance assessed by the investigator using a 4-point scale (very satisfactory, satisfactory, not very satisfactory, unsatisfactory). • Ocular tolerance assessed by the patient using a 4-point scale (very satisfactory, satisfactory, not very satisfactory, unsatisfactory).
Primary Performance Endpoint	
The primary performance endpoint is the change from baseline^a (D1) to D36 in the CLDEQ-8 total score*.

Secondary Performance Endpoints	
 • Change from baseline^a (D1) in CLDEQ-8 total score* at D15. • Soothing sensation just after instillation (less than 5 minutes)* at D15 and D36.

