Schedule of Assessments	Please refer to the Table 2 Schedule of Visits and Procedures .

Table 2 Schedule of Visits and Procedures

	Visit#1 Inclusion Visit (D1, afternoon)	Visit#2 D15 (±1 day), afternoon ⁽¹⁾	Visit#3 Final visit ⁽¹⁾ D36 (+3 days), afternoon or premature discontinuation visit ⁽²⁾
Informed consent	X		
Demography	X		
Contact lens history	X		
Ocular and Systemic Medical and Surgical History (including dry eye)	X		
Previous and Concomitant Ocular/Non-ocular Treatments	X	X	X
CLDEQ-8 self-questionnaire ⁽³⁾	X	X	X
Soothing sensation just after (less than 5 min) IMD instillation ⁽³⁾		X	X
OSDI self-questionnaire ⁽³⁾	X	X	X
Ocular discomfort evaluation (VAS) ⁽³⁾	X	X	X
Ocular symptoms throughout the day ⁽³⁾	X	X	X
Contact lens wearing time	X	X	X
Far Best Corrected Visual Acuity (BCVA) ⁽⁴⁾	X		X
Slit Lamp Examination ⁽⁴⁾	X	X	X
Conjunctival Hyperaemia (Mc Monnies photographic scale) ⁽⁴⁾	X	X	X
TBUT ⁽⁴⁾	X	X	X
Oxford 0-15 grading scheme (corneal and conjunctival staining by fluorescein with a yellow filter) ⁽⁴⁾	X	X	X

	Visit#1 Inclusion Visit (D1, afternoon)	Visit#2 D15 (± 1 day), afternoon ⁽¹⁾	Visit#3 Final visit ⁽¹⁾ D36 (+3 days), afternoon or premature discontinuation visit ⁽²⁾
Schirmer Test (without anaesthesia) ⁽⁴⁾	X	X	X
Adverse Events		X	X
Device deficiency		X	X
Urine Pregnancy Test	X		X
Verification of Inclusion and Exclusion Criteria	X		
Ocular tolerance assessment by the patient ⁽³⁾		X	X
Ocular tolerance assessment by the investigator ⁽⁴⁾		X	X
Performance assessment by the investigator ⁽⁴⁾		X	X
Training of the patient for diary completion	X	X	
Patient diary dispensation	X	X	
IMD Dispensation	X		
IMD Compliance / Patient diary completion review		X	X
Record of used/unused IMDs (in Treatment Kit Tracking Form)			X

1) No IMD instillation at least 2 hours before visit#2 and visit#3.

2) If premature discontinuation, **also** collect the new treatment for the dry eye (if applicable) with the start date and the dosing.

3) These questionnaires and VAS must be answered by the patient at the beginning of the visit (before examination).

4) Ophthalmological examinations and assessments **MUST** be performed by the **SAME** investigator.

TABLE OF CONTENTS

1	GENERAL.....	1
1.1	Identification of the Clinical Investigation Plan (CIP)	1
1.1.1	Clinical Investigation References	1
1.1.2	CIP Amendments.....	2
1.1.3	Abbreviations and Acronyms	4
1.2	Sponsor	6

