- Soothing sensation just after (less than 5 minutes) instillation,
- OSDI self-questionnaire,
- Ocular discomfort evaluation (VAS),

- Ocular symptoms throughout the day,
- Contact lens wearing time,
- Measurement of Far BCVA*,
- Slit lamp examination* for measuring:
 - conjunctival hyperaemia* with McMonnies photographic scale
 - TBUT*,
 - Oxford 0-15 grading scheme* (corneal and conjunctival staining by fluorescein with a yellow filter).
- Schirmer test* (without anaesthesia),
- AE reporting,
- Device deficiencies reporting,
- Urine pregnancy test (if applicable) (to be done at any time during the visit),
- Ocular tolerance assessment by the patient,
- Ocular tolerance assessment by the investigator*,
- Performance assessment by the investigator*,
- IMD Compliance / Patient diary completion review,
- Record of used and unused IMDs (in Treatment Kits Tracking Form),
- Status of the patient.

*Ophthalmological examinations and assessments **MUST** be performed by the **SAME** investigator.

6.1.6.3 *Additional/Optional Visit(s) during the clinical investigation*

Not Applicable

6.1.6.4 *Premature discontinuation Visit during the clinical investigation*

A patient who prematurely discontinues from the investigation should have, if possible, a premature discontinuation visit. This last site visit should take place as soon as possible after the patient stops taking IMD. All follow-up procedures and examinations scheduled to be performed at the final visit should be performed at the patient's premature discontinuation visit.

If the patient is tested COVID-19 positive during the study, the patient must inform the investigator. Either the patient may continue the clinical investigation when he/she can follow the CIP requirements safely and in accordance with the national/regional recommendations or the patient may be withdrawn from the clinical investigation.

Note: Included patients who withdraw will not be replaced by another patient. The patient number and associated inclusion number of the withdrawn patient must not be reassigned to a different patient.

6.1.6.5 *Additional Follow-Up Visit(s) (after the end of the treatment)*

Not Applicable

6.1.6.6 *Adaptive Follow-Up of Patients Prematurely Withdrawn due to an Exceptional Circumstance (e.g. COVID-19 pandemic)*

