
 To assess the safety of T2769 in contact lens wearers with dry eye symptoms. 	
 Treatment-Emergent Adverse Event (TEAE) by System Organ Class (SOC) and Preferred Term (PT) (separately for ocular and systemic TEAE). Change from baseline in Far Best Corrected Visual Acuity (BCVA) expressed in Log MAR at D36 separately in the studied eye and in the contralateral eye. Ocular tolerance assessed by the investigator at D15 and D36. Ocular tolerance assessed by the patient at D15 and D36.

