5.2 Data Derivations

Baseline and Change from baseline

Baseline and change from baseline will be calculated for all assessments as follows:

- Baseline value is defined as the assessment at inclusion visit before the first IMD instillation.
Missing value at inclusion visit will not be replaced.

- Change from baseline will be calculated as the difference between the assessment value and the baseline value.
- Change from baseline in classes will be defined as follows in three classes compared to 0:
 - Improvement (Decrease of score from baseline): Change from baseline < 0,
 - Stable: Change from baseline = 0,
 - Worsening (Increase of score from baseline): Change from baseline > 0.

Study Day

Study day will be calculated as (assessment date - date of first IMD) for pre-baseline assessments and [(assessment date - date of first IMD) + 1] for post-baseline assessments, e.g., there will be no study day 0 and study day 1 will correspond to the first IMD.

Age

Age (years) will be calculated in classes as: < 65, \geq 65 and < 85, \geq 85 years.

Time since DED diagnosis

Time since DED diagnosis (months) will be calculated as (Date of inclusion visit - Date of diagnosis) / 365.25 x 12.

If the day is missing and month is present the 15 of the month will be used. If year is present and day and month are missing, the time since DED diagnosis will be calculated as (Year of inclusion visit - Year of diagnosis) x 12.

Duration of exposure

Duration of exposure (days) will be calculated as (Date of last instillation - Date of first instillation) + 1.

If the day or the month is missing for one of the dates, the duration of exposure will be missing.

Number of days with instillation of T2769

Number of days with instillation will be calculated for both eyes together as follows:

- From D1 to D15: (Date of Visit #2 - Date of inclusion Visit + 1) - (Number of days without instillation of IMD recorded in the eCRF at Visit #2).
- From D15 to D36: (Date of Visit #3 - (Date of Visit #2 + 1) + 1) - (Number of days without instillation of IMD recorded in the eCRF at Visit #3).
- From D1 to D36: Sum of number of days with instillation from D1 and D15 and from D15 and D36.

CCI

Sponsor: Laboratoires Théa

Protocol: LT2769-003

Statistical Analysis Plan: V1.0 / 26-OCT-2023

CLDEQ-8 total Score

CCI

OSDI

CCI

Total score of ocular symptoms throughout the day

CCI

Mean contact lens wearing time as mean number of days/week

CCI

TBUT

CCI

Total ocular surface staining grade

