7.2 Patient Disposition

Patient disposition data will be presented overall.

The number of enrolled patients will be presented overall. The number (%) of patients included in each other analysis set (Safety set, FAS and PPS) will be presented overall.

The number (%) of patients by centre will be presented overall, for FAS and PPS.

The number (%) of patients per visit as considered in the analysis (i.e., after remapping of the premature discontinuation visit) will be described overall for FAS and PPS.

A listing of patients with information on analysis sets and studied eye will be produced for the enrolled patients and a listing of actual visits and visits as considered in the analysis (see Section 5.1) will be produced for the FAS.

The number (%) of patients who prematurely discontinued the study and the primary reason for discontinuation will be presented overall for the Safety Set and FAS. The number (%) of patients who prematurely discontinued the IMD and the primary reason for discontinuation will be presented overall for the Safety Set and FAS. A listing will be produced on the Safety Set presenting the patients who prematurely discontinued the study or the IMD with the detailed reason for discontinuation.

A listing of patients excluded from FAS, PPS or Safety set, presenting the reason for exclusion, will be produced on the enrolled patients.

CCI

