7.10.2 Device Deficiency

7.10.3 Far BCVA

Far BCVA in LogMar will be described at each assessment time (baseline, and D36) for the studied eye and the contralateral eye. Change from baseline at D36 will be described as well.

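### Does the SAP's remapping rule lose the visual acuity of patients who stop before Visit 2?

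*SAP*

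**What the plan says.** Protocol 6.1.6.4 asks for a visit, if possible, when a patient stops early: "All follow-up procedures and examinations scheduled to be performed at the final visit should be performed" then. Table 2 gives the final visit and the discontinuation visit one shared column. Far BCVA is marked in that column and at Visit 1, but not at Visit 2. Protocol 6.4.1.3.1 likewise plans acuity at D1 and D36 only.

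SAP 5.1 supplies the allocation rule: "Data from premature discontinuation visit will be allocated to the next planned visit unless the scheduled visit is performed after discontinuation visit". SAP 7.2 then counts "patients per visit as considered in the analysis (i.e., after remapping of the premature discontinuation visit").

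The safety endpoint in SAP 4.1 is "Change from baseline in Far Best Corrected Visual Acuity (BCVA) expressed in Log MAR at D36", separately for the studied and the contralateral eye. SAP 7.10.3 matches it: "Far BCVA in LogMar will be described at each assessment time (baseline, and D36) for the studied eye and the contralateral eye", with the change described at D36. SAP 5.2 states that "Baseline and change from baseline will be calculated for all assessments as follows". The Far BCVA paragraph later in that section is blacked out.

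**The concern.** A patient who stops before Visit 2 and attends the site has acuity measured at the discontinuation visit. SAP 5.1 sits under a visit-windowing heading, and SAP 7.2 speaks of remapping the visit. A programmer could fairly give the whole record one label, D15. The acuity value would then have a baseline and a computable change, but no row in the visible Far BCVA summary. A patient who stops after Visit 2 would have acuity counted at D36.

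At stake is the completeness of a listed safety endpoint among people who stop early, a group of natural interest for tolerability. Two programmers could also produce different D36 acuity tables from the same data.

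**Working it through.** No sample-size or power figure is involved. The check is a count and a trace of the rule.

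**1. How many parameters are exposed?** The protocol synopsis lists 11 performance and 6 safety parameters: 11 + 6 = 17. Against Table 2, 16 of these are scheduled at Visit 2. The exception is "Far BCVA in each eye".

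Three of the 17 have no results by visit, so remapping does not bear on them. Ocular and systemic adverse events are tabulated by system organ class and preferred term (SAP 7.10.1), and device deficiencies are only listed (Protocol 7.2.2). The meaningful denominator is 17 − 3 = 14, and Far BCVA is 1 of 14.

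**2. Where does the rule send acuity?**

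| Discontinuation visit | Rule applied to the whole visit | Rule applied per assessment |
|---|---|---|
| Before Visit 2 (e.g. Day 5 or 10) | D15: not in the acuity summary | D36: in the summary |
| After Visit 2 (e.g. Day 20 or 30) | D36: in the summary | D36: in the summary |

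The readings differ only in the first row.

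**3. Which reading does the text support?** The subject of the SAP 5.1 sentence is data, and D36 is the only post-baseline time planned for acuity in Table 2, Protocol 6.4.1.3.1 and SAP 7.10.3. That favours the second column. The wording of SAP 7.2 favours the first, but it describes a disposition count and does not say how to place a measurement never planned at D15. The visible text leaves both open.

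**4. Is the first column wrong?** The endpoint is defined at D36, and Protocol 7.13 has safety analysed as observed. A value taken before Visit 2 is not a D36 observation, so omitting it from a D36 summary agrees with the endpoint.

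**5. How sharp is the contrast between patients?** Suppose Visit 2 is due on Day 15. A stop visit on Day 14, before Visit 2, maps to D15 on the whole-visit reading. A stop visit on Day 16, after Visit 2, maps to D36, although it is 36 − 16 = 20 days early. That pair is chosen at the boundary. A stop visit on Day 35 is 36 − 35 = 1 day early. The contrast comes from the general rule, which treats every parameter measured after Visit 2 in the same way.

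**6. Who is affected?** Only treated patients who have an on-site discontinuation visit before Visit 2 and do not attend the scheduled visit afterwards. The telephone discontinuation procedure in Protocol 6.1.6.6 includes no acuity measurement. The documents give no count for this group, and it may be zero.

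**The case for a change.** The best case for a change is that the visible SAP does not say which reading applies, and that a value the protocol asks for should have a stated place in the analysis. One clause in SAP 5.1 would settle it. A row for the last on-study acuity, with its change from baseline, would show every patient measured after treatment started.

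The first part stands: the visible text is ambiguous, and Far BCVA is the one by-visit parameter where this matters. It does not establish that the rule is absent, because the paragraph where it would most naturally sit is blacked out.

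The extra row is weaker. It would be a last-observation summary that neither document lists as an endpoint. On the per-assessment reading it would largely repeat the D36 row.

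Other safeguards limit what could be lost. Protocol 6.4.1.3.2 makes clinically significant worsening of a pre-existing sign or symptom reportable as an adverse event. SAP 7.1 plans listings of all individual data, although its visible categories do not name acuity. SAP 7.2 lists actual against analysed visits for the full analysis set, so any remapping can be traced.

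**Conclusion.** No change to the plan is called for. This is a small gap in detail that analysts can fill sensibly, provided one reading is fixed before the tables are run and applied to every patient. Either choice is defensible: one keeps the D36 summary closer to D36, the other keeps all measured patients in it. Neither yields a wrong result.

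The size is 1 of 14 by-visit parameters, in one descriptive table, for a number of patients that the documents do not give. No direction of effect can be stated, and no hypothesis test, performance endpoint or adverse event table depends on it.

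This rests on two assumptions: that nothing in the blacked-out SAP text forces a worse allocation, and that clinically significant acuity losses are reported as adverse events as the protocol requires. If the Far BCVA derivation in SAP 5.2 already states the rule, the question disappears.

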5.2 Data Derivations

Baseline and Change from baseline

Baseline and change from baseline will be calculated for all assessments as follows:

- Baseline value is defined as the assessment at inclusion visit before the first IMD instillation.
Missing value at inclusion visit will not be replaced.

- Change from baseline will be calculated as the difference between the assessment value and the baseline value.
- Change from baseline in classes will be defined as follows in three classes compared to 0:
 - Improvement (Decrease of score from baseline): Change from baseline < 0,
 - Stable: Change from baseline = 0,
 - Worsening (Increase of score from baseline): Change from baseline > 0.

Study Day

Study day will be calculated as (assessment date - date of first IMD) for pre-baseline assessments and [(assessment date - date of first IMD) + 1] for post-baseline assessments, e.g., there will be no study day 0 and study day 1 will correspond to the first IMD.

Age

Age (years) will be calculated in classes as: < 65, \geq 65 and < 85, \geq 85 years.

Time since DED diagnosis

Time since DED diagnosis (months) will be calculated as (Date of inclusion visit - Date of diagnosis) / 365.25 x 12.

If the day is missing and month is present the 15 of the month will be used. If year is present and day and month are missing, the time since DED diagnosis will be calculated as (Year of inclusion visit - Year of diagnosis) x 12.

Duration of exposure

Duration of exposure (days) will be calculated as (Date of last instillation - Date of first instillation) + 1.

If the day or the month is missing for one of the dates, the duration of exposure will be missing.

Number of days with instillation of T2769

Number of days with instillation will be calculated for both eyes together as follows:

- From D1 to D15: (Date of Visit #2 - Date of inclusion Visit + 1) - (Number of days without instillation of IMD recorded in the eCRF at Visit #2).
- From D15 to D36: (Date of Visit #3 - (Date of Visit #2 + 1) + 1) - (Number of days without instillation of IMD recorded in the eCRF at Visit #3).
- From D1 to D36: Sum of number of days with instillation from D1 and D15 and from D15 and D36.

CCI

Sponsor: Laboratoires Théa

Protocol: LT2769-003

Statistical Analysis Plan: V1.0 / 26-OCT-2023

CLDEQ-8 total Score

CCI

OSDI

CCI

Total score of ocular symptoms throughout the day

CCI

Mean contact lens wearing time as mean number of days/week

CCI

TBUT

CCI

Total ocular surface staining grade

CCI

Far BCVA

CCI

Adverse event (AE) time to occurrence

Time to AE occurrence (days) will be calculated as Date of onset – Date of IMD instillation.

CCI

Published date: 29Mar2023

Effective date: 12Apr2023

CONFIDENTIAL

Page 12 of 24

AE duration

Duration (days) of an AE will be calculated as (Date of recovery – Date of onset) + 1.

5.3 Other Data Analyses Considerations

Strata and Covariates

Not Applicable.

Multiple Comparisons and Multiplicity

There is a single primary performance endpoint in the study (change from baseline to D36 in the CLDEQ-8 total score). Other performance measures are defined as of secondary importance. Thus comparison will be performed at a two-sided significance level of CCI; no adjustment of the type I error rate will be made.

6 Analysis Sets

Analysis sets to be used for the analyses are described in the table below.

Table 1: Analysis Sets

Analysis Set	Description
Enrolled set	All patients who have signed the informed consent form and for whom the inclusion visit has been recorded in the eCRF.
Safety set	All enrolled patients, having received at least one instillation of IMD. The safety set will be the primary population for the safety analysis.
Full-Analysis set (FAS)	All enrolled and included (i.e., started the treatment period) patients, having received at least one instillation of IMD and with at least one baseline and one post-baseline performance assessment. The FAS will be the primary population for the performance analysis.

Analysis Set	Description
Per-protocol set (PPS)	
Subset of the FAS including patients without any major clinical investigation plan (CIP) violations likely to seriously affect the primary outcome of the study.
 
Deviations from CIP will be detailed in a separate document and assessed as “minor” or “major” during data review meeting before the database lock.
 
The PPS will be considered as a secondary population and will be used for sensitivity analyses of the primary and secondary endpoints.

7 Methods of Analysis

7.1 General Considerations

Statistical analyses will be performed by the Biostatistics unit of CCI. Analyses will be conducted with SAS Studio 5.2 under SAS Viya 3.5 (SAS Institute, North Carolina, USA).

Continuous data will be described in summary tables presenting, overall, the number of non-missing observations (n), mean, standard deviation (SD), median, lower quartile (Q1), upper quartile (Q3), minimum and maximum, and 95% Confidence Interval (CI) of the mean/median.

Categorical data will be described in summary tables presenting, overall, the number of non-missing observations (n), count and percentage of each modality, and 95% CI.

95% CI of a proportion will be calculated using the scoring method of Wilson without continuity correction:

$$\text{Lower Limit} = \frac{2np + z^2 - z\sqrt{z^2 + 4npq}}{2(n + z^2)} \quad \text{Upper Limit} = \frac{2np + z^2 + z\sqrt{z^2 + 4npq}}{2(n + z^2)}$$

with n = number of non-missing observations

p = percentage

q = 1 - p

z = 1.96 for two-sided 95%CI

Except for minimum and maximum, descriptive statistics will be presented with one more decimal than the recorded value.

For all variables, the number of missing values will also be reported in the tables, but they will not be counted for the percentage calculation (categorical data).

Parameters recorded for both eyes will be described separately for the studied eye and for the contralateral eye.

The acceptable risk of error for the statistical tests will be set at 5%.

CCI

Tables and Listings will be provided in separated documents (Word and PDF files) except the listing of Deaths, Other Serious Adverse Events, discontinuations due to Adverse Events and other Adverse Events of Special Interest (if applicable) which will also be provided in Excel format (see Section 7.10.1).

All individual data will be described in the patient data listings CCI [REDACTED] by patient as follows: discontinued patients, protocol deviations, patients excluded from the performance analysis, demographic data and baseline characteristics, compliance/exposure, individual performance response data, adverse events (AEs) listings.

